### 9.2.0 Adverse Event Severity grading

Adverse event toxicity will be graded according to the defined NCI Toxicity scales (Appendix C) and appropriate action taken. Adverse events not included in the defined NCI toxicity criteria will be graded according to their effects on the daily activity of the study subjects:

- Grade 1: No limitation of daily activity
- Grade 2: Some limitation of daily activity
- Grade 3: Severe limitation of daily activity

#### **9.4.0 Potential Expected Adverse events**

The biopsies required for the study are not expected to appreciably increase the small risk of serious adverse events that might otherwise happen during or after rectal endoscopic procedures. These potential risks can include bleeding and bowel perforation. The risk of perforation is expected to be lower in the rectal region than to what expected with higher colonic biopsies.

Possible side-effects with celecoxib can include: diarrhea, indigestion, headache; nasal congestion, sore throat, rhinorrhea and/or upper respiratory tract infection; abdominal pain, stomach pain, peptic ulcer disease, gastrointestinal bleeding, gas, nausea, back pain; extremity edema, dizziness, insomnia, tinnitus, liver function test abnormalities, hepatitis, jaundice, and/or rash. Celecoxib at a dose of 800 mg daily was found to increase risk of major fatal and non-fatal cardiovascular events by 3.4-fold compared to subjects who were taking placebo in the Adenoma Prevention with Celecoxib (APC) trial (<http://www.fda.gov/cder/drug/infopage/celebrex/celebrex-hcp.htm>). One incident of rhabdomyolysis has been reported in a patient taking celecoxib. The possibility of celecoxib being the cause of this incident cannot be excluded.

#### **9.5.0 Measures to monitor side effects and manage adverse events**

Subjects will be observed for at least 60 minutes after biopsy procedures. Contact telephone numbers will be provided to ensure that medical staff may be easily reached. Subjects are asked to call in case of excessive bleeding or abdominal pain after the procedure. If excessive bleeding is evident after the procedure, the lesions will be cauterized. Surgical backup is available at all times.

Study subjects will be contacted by phone 72 hr after the first celecoxib doses and every 2 weeks thereafter for the rest of the celecoxib treatment duration for toxicity assessment. In addition, subjects will undergo a history and physical to assess for toxicity during a clinical visit at the end of the treatment. All adverse events will be followed according to good medical practices. "Unacceptable toxicity for a chemoprevention agent is defined as any Grade 3 or higher toxicity (NCI Common Toxicity Scale) for any of the listed categories or Grade 2 or higher allergic reaction or cardiac toxicity." If a study investigator determines that an unacceptable toxicity [Grade 3 or higher toxicity for any of the NCI Common Toxicity Scale categories or Grade 2 or higher allergic reaction or cardiac toxicity] is possibly related to celecoxib, then celecoxib will be stopped and the study Chair be informed. The PI will meet with Drs. [name] (study co-investigators) and [name] (study biostatistician) to perform a cumulative review of all adverse events and premature terminations every 6 months after study initiation or after completion of 15% of subject enrollment (enrollment of 6 patients). If any cardiovascular adverse event is identified for a follow-up period, [name], the study collaborating cardiologist, will participate in the review of the cumulative toxicity. The patient will be followed up according to good medical practices. As a part of the follow-up in case of unacceptable toxicity development, a telephone contact will be made at 30  $\pm$  7 days after celecoxib discontinuation to assess the resolution of the adverse event(s).

#### **9.5.1 Clinical Research Compliance's Monitoring of the Conduct of the Study and the Safety of Participants**

This monitoring schedule will occur once every 6 months or for every 15% of newly registered patients, whichever occurs first. The monitoring team will consist of one or more staff members from the Clinical Research Compliance, depending on the rate of accrual of patients. In addition, two or three faculty members with clinical research experience and expertise in the disease site of the protocol serve as the medical reviewers on the monitoring team. These medical reviewers, like the other members of the team, are independent and objective. They cannot be collaborators on the study or members of the same academic department as the PI, and they cannot have any other involvement with the study. (The members of the Clinical Research Compliance have no such conflicts because they are independent of all academic departments in the institution.)

The monitoring teams review the following elements for each study they monitor: informed consent forms, eligibility, pretherapy requirements, treatment administration, evaluations during the study and at follow-up, all toxic effects, response to therapy, and general data quality. In addition, the monitoring teams use the PDMS to generate a report so they can review all adverse events—serious, not serious, expected, and unexpected—reported by each study participant, not just those reported in the charts of participants selected for in-depth review. The information in this PDMS-generated report includes the date of onset of the event, its severity grade, its suspected causal relationship with the treatment, the date the event resolved, and whether the event required treatment.

A pre-activation meetings will be held with the PIs, their research teams, and representatives of the Clinical Research Compliance to discuss the data and safety monitoring plan for the trials. The monitoring plan is discussed, and templates for data collection are distributed. These templates are prepared by the Clinical Research Compliance case by case after their review of the study protocol. After the templates are completed by the research team, they become a permanent part of the study participants' medical records.

A report is prepared by the monitoring team after each monitoring visit. The completed report is given to the research team, which has 1 week to review the report and provide any data identified as missing by the monitoring team. A final monitoring report is then prepared. If the report does not indicate the occurrence of unexpected adverse events or issues of noncompliance with Current Good Clinical Practice, federal regulations, or institutional policies, it is reviewed by the Clinical Research Compliance Oversight Committee. If a monitoring report indicate such occurrence or issues, it is forwarded to the IRB for review and action.

#### **9.6.0 Serious Adverse Events**

Serious Adverse Experience -Any adverse drug experience that results in any of the following outcomes:

- Death

- A life-threatening adverse drug experience - any adverse experience that places the patient, in the view of the initial reporter, at immediate risk of death from the adverse experience as it occurred. It does not include an adverse experience that, had it occurred in a more severe form, might have caused death.

- Inpatient hospitalization or prolongation of existing hospitalization
- A persistent or significant disability/incapacity - a substantial disruption of a person's ability to conduct normal life functions.
- A congenital anomaly/birth defect.

Important medical events that may not result in death, be life-threatening, or require hospitalization may be considered a serious adverse drug experience when, based upon appropriate medical judgment, they may jeopardize the patient or subject and may require medical or surgical intervention to prevent one of the outcomes listed in this definition. Examples of such medical events include allergic bronchospasm requiring intensive treatment in an emergency room or at home, blood dyscrasias or convulsions that do not result in inpatient hospitalization, or the development of drug dependency or drug abuse.

#### **9.7.0 Reporting Serious Adverse Events**

All serious adverse events, whether they appear to be related to the study medication or not, will be reported to the study chair and the MD Anderson IRB (via OPR) within 24 hours of knowledge of the event.

#### **9.7.1 Reporting procedure for cardiovascular toxicity**

If an adverse cardiovascular event is identified, the research nurse will notify the PI within 24 hours. The PI will report all grade 2 or more adverse cardiovascular events related to the study to the IRB within 1 working day of his notification about the event. All serious cardiac adverse events will be reported to the FDA through the FDA Medical products Reporting Program (Med Watch) using the on line reporting mechanism within 3 working days.

#### **9.8.0 Early stopping role for cardiovascular toxicity**

The proportion of subjects who developed serious cardiovascular adverse events while taking placebo was reported as 1.8 % in a large international study for the prevention of sporadic polyps, the Prevention of Spontaneous Adenomatous Polyps Trial. Based on this information, we have statistically estimated the numbers of cardiovascular events that will predict that celecoxib will have excessive cardiovascular toxicity (10.3.7). According to these calculations, we will suspend the study for excessive cardiovascular toxicity if 2 or more of the first 10 patients enrolled on the trial experience a grade 2 or greater cardiovascular toxicity, or if 3 or more of the first 31 patients experience a grade 2 or greater cardiovascular toxicity, or if at any time during the study a 4th patient experiences a grade 2 or greater cardiovascular toxicity. The study will be suspended by stopping enrollment of new subjects and celecoxib treatment for all enrolled patients. If the study is suspended, the IRB and NCI will be notified within 3 working days. The following study clinical investigators will review safety data: Drs. [name] and [name] in consultation with [name], study biostatistician and [name], collaborating cardiologist. A report of this safety review will be sent to MD Anderson IRB and the NCI. The study will be permanently stopped unless the MD Anderson IRB, NCI and study investigators all agree that the study can be safely resumed.

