### **7.3.0 Enrollment on the study**

The informed consent will be reviewed and discussed with subjects who are approached for enrollment on the study. A potential study candidate who is interested in enrollment can be provided with a copy of the informed consent to review at home. If after returning home, a potential study candidate expresses interest in enrolling in the study but is unable to be physically present at MD Anderson at the time of signing the informed consent due to physical distance, he or she may fax the signed consent form to a clinical study investigator and mail the original at the same time. The subject will be enrolled on the study once a clinical study investigator has signed the informed consent. In addition, before the patient starts his or her colonic procedure the patient will then be re-consented by the clinical study investigator. After signing an informed consent, each subject will complete a demographic data forms including the following information: Age, Sex, diagnosis, registration number, telephone number and address. Subjects will also complete questionnaires regarding medications, vitamins, dietary food questionnaire, and nutritional supplements (Appendix H). The original copy of the consent form will be filed in the patient's medical records. A copy of the consent will be kept in the patient's study file, and a second copy will be given to the patient. In the event that the patient has an opportunity to qualify for other research studies, the patient may sign up two different consents. Once the patient is determined non-evaluable during the initial colonic procedure (having less than 20 polyps), the patient will be enrolled on an alternative research study that require the patient to have less than 20 polyps on their initial colonoscopy.

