### **7.4.0 Celecoxib administration**

Following the initial colonoscopy procedure, subject will start celecoxib at a dose of 400 mg po bid with meals. Celecoxib treatment will be continued for 6 months.

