### 10.3.7 Estimation of celecoxib excessive cardiovascular toxicity

We will use the design of Thall and Simon (1994) to continuously monitor grade 2 cardiovascular toxicities, with the trial suspended if the rate is deemed too high, the data reviewed, and only opened again after review by the NCI and IRB.

Let  $P$  represent the proportion of patients in the trial who experience at least one cardiovascular toxicity of grade 2 or higher during the 6 months on study drug. We will continuously monitor this quantity in the trial using the method of Thall and Simon (1994). We assume a diffuse prior distribution on  $P$ , specifically a Beta (0.02, 0.98), which has mean 0.02 and 95% credible interval (0,0.28). We will suspend accrual in the trial if, at any time during the trial,  $\Pr(P > 0.018) > 0.90$ . That is, we will stop the trial early if, based on the data in the trial, there is strong evidence (probability > 0.90) that the grade 2 cardiovascular toxicity rate is greater than 0.018. Based on this criterion, the trial will be terminated early for excessive toxicity if 2 or more of the first 10 patients enrolled on the trial experience a grade 2 or greater cardiovascular toxicity, or if 3 or more of the first 31 patients experience a grade 2 or greater cardiovascular toxicity, or if at any time during the study a 4th patient experiences a grade 2 or greater cardiovascular toxicity. With these stopping rules, the study will suspend accrual of new patients and celecoxib treatment of enrolled patient with probability 0.85 if, in fact,  $P=0.10$ , and with probability 0.46 if, in fact,  $P=0.05$ . If the true proportion is  $P=0.01$ , then the trial will stop with probability 0.04. (see reference 35).

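### The first cardiovascular stopping window counts enrolled patients, enrolment is fixed at consent, and the monitored rate is toxicity on drug: a small ambiguity to fix when the stopping probabilities are restated

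*Combined protocol and SAP*

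**What the plan says.** The rule has three limbs, printed in both 9.8.0 and 10.3.7.

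- First limb: suspend "if 2 or more of the first 10 patients enrolled on the trial experience a grade 2 or greater cardiovascular toxicity".
- Second limb: 3 or more events in the first 31 patients. The word enrolled is not repeated.
- Third limb: a 4th event at any time, with no denominator.

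Section 7.3.0 gives enrolment a date: "The subject will be enrolled on the study once a clinical study investigator has signed the informed consent". Treatment comes later, under 7.4.0: "Following the initial colonoscopy procedure, subject will start celecoxib at a dose of 400 mg po bid with meals". Between the two, 7.3.0 foresees some patients leaving: "Once the patient is determined non-evaluable during the initial colonic procedure (having less than 20 polyps"), the patient moves to an alternative study.

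Section 10.3.7 takes as its monitored quantity P the share of trial patients "who experience at least one cardiovascular toxicity of grade 2 or higher during the 6 months on study drug". It sets a Beta(0.02, 0.98) prior and a posterior criterion, Pr(P > 0.018) > 0.90, to be applied continuously ("We will suspend accrual in the trial if, at any time during the trial"). It presents the three limbs as the result and states that the study will be suspended with probability 0.85, 0.46 and 0.04 at P = 0.10, 0.05 and 0.01.

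**The concern.** A patient who never takes celecoxib cannot have a toxicity on study drug. If such a patient holds one of the first 10 places, the window covers fewer than 10 people at risk, and the undosed patient counts as if observed free of toxicity. The error runs towards not stopping.

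It can change the answer. Suppose 2 of the first 11 enrolled are never dosed, and the second event falls in the 9th treated patient, who is the 11th enrolled. In dose order that is 2 events in 9 patients, so the first limb is met. In enrolment order the event lies outside the first 10, so it is not met. Two careful readers of one dataset would disagree. The study dose, 800 mg daily, is the one for which 9.4.0 cites a 3.4-fold cardiovascular risk, so the rule should have one reading.

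**Working it through.** **Inputs.** The three limbs, the prior and the criterion come from 9.8.0 and 10.3.7; the sample size of 40 from 3.0. The documents give no share of enrolled patients who are never dosed. I call it u and assume 10%, 20% and 30%, with 0% as reference.

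**Step 1. The plan's own figures, everyone dosed.** Let S10, S31 and S40 be the events in the first 10, 31 and 40 patients, binomial with rate P. Then

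P(stop) = P(S10 ≥ 2) + P(S10 ≤ 1, S31 ≥ 3) + P(S10 ≤ 1, S31 ≤ 2, S40 ≥ 4).

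- P = 0.10: 0.2639 + 0.3687 + 0.0518 = 0.684 (stated 0.85)
- P = 0.05: 0.0861 + 0.1400 + 0.0198 = 0.246 (stated 0.46)
- P = 0.01: 0.0043 + 0.0027 + 0.0001 = 0.007 (stated 0.04)

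The stated probabilities do not reproduce from the printed counts.

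**Step 2. What the criterion gives.** With x events in n patients the posterior is Beta(0.02 + x, 0.98 + n − x). Pr(P > 0.018) exceeds 0.90 with 2 events up to n = 30 (0.902; 0.896 at n = 31) and with 3 events up to n = 62, which is any time in a 40-patient trial. For a rule of 2 events by n = 30 or a 3rd at any time,

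P(stop) = P(S30 ≥ 2) + P(S30 = 1)·P(≥2 in the last 10) + P(S30 = 0)·P(≥3 in the last 10).

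- P = 0.10: 0.8163 + 0.0403 = 0.857
- P = 0.05: 0.4465 + 0.0317 = 0.478
- P = 0.01: 0.0361 + 0.0010 = 0.037

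These are close to the stated 0.85, 0.46 and 0.04. The criterion alone would also suspend on 1 event up to n = 6 (0.902).

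**Step 3. One undosed patient in the first window.** At P = 0.10, P(≥2 events) is 1 − 0.9^10 − 10(0.1)(0.9^9) = 0.264 with 10 at risk, and 1 − 0.9^9 − 9(0.1)(0.9^8) = 0.225 with 9.

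**Step 4. The whole printed rule.** Exact recursion over enrolled, dosed and events: each enrolled patient is never dosed with probability u, accrual runs to 40 dosed, and the limbs are checked at each event.

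| P | Windows in enrolment order | u = 0 | 10% | 20% | 30% |
|---|---|---|---|---|---|
| 0.10 | first only | 0.684 | 0.681 | 0.679 | 0.676 |
| 0.10 | both | 0.684 | 0.659 | 0.637 | 0.620 |
| 0.05 | first only | 0.246 | 0.242 | 0.238 | 0.234 |
| 0.05 | both | 0.246 | 0.221 | 0.200 | 0.182 |

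The first-only rows apply enrolment order just where the text uses the word. The both rows assume that the second window inherits it.

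**The case against.** The strongest reply is that the documents nearly settle the denominator. P is defined on drug and the counts are said to follow from it. Section 7.1.0 recruits patients who will be undergoing celecoxib treatment, and 9.1.0 defines an adverse event as arising after the drug is started. Section 9.8.0 describes suspension as "stopping enrollment of new subjects and celecoxib treatment for all enrolled patients", which treats enrolled patients as patients on drug. Section 9.5.0 schedules a review "after completion of 15% of subject enrollment (enrollment of 6 patients"), and 6 is 15% of the 40-patient sample. This stands as evidence of intent, and I accept that dosed patients were probably meant. It does not remove the express definition of enrolment in 7.3.0.

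It also stands that u is assumed. That patients with fewer than 20 polyps leave undosed is the natural inference, but no section says so. The cap at 40 dosed also matters: 7.12.0 replaces non-completers, so more than 40 may be dosed, and the 4th-event limb then recovers part of the loss. At P = 0.10, u = 20% and both windows by enrolment, the loss is 4.7 points with 40 dosed, about 3 with 45 and about 1.8 with 50.

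Three stronger readings are tempting and not supported:

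- A reader might infer that all the limbs count by enrolment. Only the first says so, and most of the larger loss in Step 4 comes from the second window.
- A reader might infer that the posterior criterion itself is defeated. In the 10-patient example it is met on either count (0.990 for 2 of 9, 0.985 for 2 of 11). It changes answer only near its two-event limit: a second event in the 28th dosed, 31st enrolled patient gives 0.913 or 0.896. The printed rule has no such limit, and 10.3.7 does not ask for undosed patients to enter the posterior.
- A reader might infer that safety monitoring is lost. The 4th-event limb, individual drug stopping and cardiologist review (9.5.0) and IRB reporting (9.7.1) do not depend on the denominator.

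**Conclusion.** The point holds as a minor ambiguity, not a contradiction. The first window is worded by enrolment, enrolment precedes drug, and the monitored rate is on drug. For an assumed never-dosed share of 10 to 30% and 40 dosed patients, the stopping probability at P = 0.10 and 0.05 falls by 0.3 to 1.2 percentage points if only the first window is affected. It falls by 2.5 to 6.4 points if both are. At a share of 0% the loss is zero.

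The gap between printed counts and stated probabilities is separate and far larger. It is present with every patient dosed, so the denominator does not explain it. It belongs here only because restated probabilities need a defined denominator.

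**What to change.** In both 9.8.0 and 10.3.7, define the 10- and 31-patient windows as patients who have received at least one dose of celecoxib, in order of first dose, and leave out enrolled patients who never start drug.

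In the same amendment, restate the stopping probabilities on that basis, in one of two ways:

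- keep the printed counts and state 0.684, 0.246 and 0.007 at P = 0.10, 0.05 and 0.01 for 40 dosed patients; or
- replace the counts with those the posterior criterion gives. Two events by n = 30 or a 3rd at any time gives 0.857, 0.478 and 0.037. State also whether 1 event in the first 6 patients suspends, as the criterion alone implies; including it gives 0.877, 0.540 and 0.082.

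The cost is a phrase in two sections, a first-dose date in the monitoring listing and revised figures. There are no extra patients or procedures. The downside is that the rule may trigger slightly earlier under the dosed count, and more readily still under the second option. Under the first option the stated chances of stopping a toxic regimen become less favourable.

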### **10.0 DATA ANALYSES**

#### **10.1.0. Data base management**

##### **10.1.1 Master Data Base**

All clinical data for the protocol will be entered into The University of Texas MD Anderson Cancer Center Protocol Data Management System (PDMS). All laboratory data will be organized into a secure master database in Microsoft access. This data set will reside on the Intel machine in the department of Clinical Cancer Prevention.

Some of the data sets will be collected at the subject level and some at the specimen level, so the appropriate index keys are used in each data set comprising the base to allow for efficient merging of the data. Following quality review, data will be merged into the master data set as it is entered (as described below).

##### **10.1.2 Derived Data Sets**

For each analysis, a data set will be built by merging appropriate sets from the master base (more than one analysis will use a given set). This data set will have records at the appropriate level of observation (e.g., subject), and will contain all of the transformations of original variables as specified above and as may be required. Provisions will be made to allow the production of derived data sets for graphics and reports that can be passed to a variety of programs on any of the major end-user platforms (DOS/Windows, Macintosh or UNIX).

